#### **1.1.4 Rationale for Consolidative Thoracic Radiation Therapy**

In a phase III study of consolidative thoracic radiation therapy for treatment of patients with ED-SCLC in the first line, participants who had any response to systemic 4-6 cycles of EP chemotherapy were enrolled in a randomized fashion to either no further treatment or to receive a 30-Gy dose of radiation delivered in 10 daily fractions to any residual intrathoracic disease including all initially involved hilar and mediastinal lymph node stations[5]. All patients also received prophylactic cranial irradiation as part of the study protocol. Baseline characteristics were typical for a SCLC population with respect to age, smoking history, and gender.

**Safety.** Consolidative thoracic radiation therapy was well tolerated in the above study. Ninety-five percent of patients completed the protocol-specified radiation therapy without interruption, with only 1 patient discontinuing treatment. The rate of grade 3 and higher toxic effects was only 10.5% compared with 7.2% in the control arm that received no thoracic radiation therapy. The incidence of grade 3 dyspnea or cough was only 1.2% in the thoracic radiation therapy group.

**Efficacy.** The multi-center study from Slotman et al. described above enrolled 498 patients. The study reported a significant improvement in PFS at 6 months (24% vs 7%, HR 0.73) and a significant improvement in 2-year OS (13% vs 3%, p=0.004) with the addition of TRT. Another randomized study by Jeremic et al., which included 206 patients with ED-SCLC who were treated with 3 cycles of EP, reported complete response at distant sites and at least a partial response in the chest [6]. Patients were randomized to thoracic radiation therapy with low-dose chemotherapy versus chemotherapy alone for 4 additional cycles. Patients who received thoracic radiation therapy reported significantly increased OS compared with chemotherapy alone (median 17 vs 11 months, 5-year OS of 9% vs 4%).

### **1.1.5 Rationale for Omission of Prophylactic Cranial Irradiation**

Prophylactic cranial irradiation (PCI) remains controversial for patients with ED-SCLC. One randomized controlled study evaluating the efficacy of PCI by Slotman et al. demonstrated a survival benefit with treatment. In that study, the hazard ratio for death was 0.68 (95% CI, 0.52-0.88) [24]. One major criticism of the study design is that brain imaging was not part of the standard staging or follow-up procedures unless neurologic symptoms were present. Given the high incidence of clinically undetected brain metastases, presumably some magnitude of benefit seen in this study could be attributable to treatment of patients with clinically undetected brain metastases.

Another more recent Japanese phase III randomized study evaluating the role of PCI in patients with ED-SCLC did enroll patients to determine whether PCI (25 Gy in 10 fractions) could affect survival [25]. In this study, brain MRI was required prior to initiation of PCI, and all patients who did not receive PCI underwent brain MRI every 3 months while enrolled on the study. The study reported a non-significant trend toward longer survival in patients who did not receive PCI (15.1 months in the control group vs. 10.1 months in the PCI group; P=0.09). On the basis of an interim analysis with these findings, the study was terminated for futility. Because patients in this study will undergo repeat staging with MRI brain prior to study enrollment after EP chemotherapy, we will not allow PCI.

Finally, recent studies suggest that anti-PD-1 therapy may penetrate the blood brain barrier to treat brain metastases in patients with NSCLC[26]. Among 11 NSCLC patients with untreated brain metastases, the brain metastasis response rate was 45% in the absence of any radiation therapy or surgical intervention. The duration of response was at least 12 weeks for 4 of 5 responders. This data suggests that treatment with immune checkpoint therapy as part of our clinical protocol may help to further reduce the incidence of clinically relevant brain metastases in patients with ED-SCLC.

### **1.1.6 Rationale for Nivolumab/Ipilimumab with Thoracic Radiation Therapy**

The excellent response rates and OS rates with combined immune checkpoint blockade in the second line treatment of ED-SCLC outlined in Section 1.1.3 demonstrates that the immune system is actively involved in

SCLC tumor pathology. However, these responses are somewhat limited to patients that have preexisting T cells primed to target the tumor. Radiation therapy (RT) by itself has demonstrated clinical efficacy in multiple malignancies, including SCLC, by improving tumor control with limited toxicity and evolving evidence suggests RT may be a promising modality to combine with immunotherapy to amplify the immune response [27].

Cancer cells treated with noxious stimuli (e.g. chemotherapy or RT) undergo various forms of cell death, which results in differential antigenic presentation and clearance by the host [28]. Accumulating evidence indicates that RT can trigger an additional type of cellular demise termed immunogenic cell death (ICD) [29]. ICD is characterized by cell surface presentation and release of cryptic antigens, which have been termed danger-associated molecular patterns (DAMPs), into the surrounding tumor microenvironment [30]. RT-induced DAMP exposure has been demonstrated in various models *in vitro* and *in vivo* and is emerging as a therapeutic approach to increase the immune response. Prior studies have demonstrated that cancer cells that were treated with RT were able to prime a durable immune response to phenotypically similar cells when challenged in the opposite flank of a mouse [31]; this effect was found to be dependent on induced DAMP exposure. RT has also been found to increase MHC I expression [32], increase ligands that promote immune activity and enhance the profile of inflammatory soluble mediators in the tumor microenvironment [33]. Thus, it is hypothesized that RT is inducing an *in situ* vaccine of the targeted tumor and is aiding in overcoming the immunosuppressive environment.

In addition to the tumor targeted with RT, a burgeoning amount of evidence indicates tumors outside of the radiation field are also affected by the generation of this locally produced *in situ* vaccine. This phenomenon, though rare, is termed the abscopal effect and is thought to be mediated by the immune system [34]. This was first demonstrated in irradiated lung cancer cells which were inoculated into the footpads of mice followed by treatment with a dendritic cell (DC) growth factor; this study identified that the combination of immune stimulation and RT led to regression of pulmonary metastases, which were outside the irradiated field, and this was dependent on an intact immune system [35]. These findings were confirmed in other model systems [36, 37] and subsequent studies demonstrated that RT also increases T cell expansion, DC activation and cytokine release [38].

Though RT alone changes the antigen repertoire of the treated tumor and influences the distribution of immune effector cells, clinically this is not sufficient to maintain robust local responses and is unable to induce the abscopal effect in the majority of scenarios. Therefore, investigators have begun to combine RT with immune checkpoint blockade to create synergism between two highly effective tumor controlling modalities. This was first examined by combining RT with CTLA-4 blockade in a breast cancer model, which demonstrated that combination treatment compared to either alone resulted in improved local and distant control of the tumor burden [39]. Also, PD-1 deficient mice or PD-1 blockade lead to an abscopal effect in melanoma and renal cell cancer models [40]. Importantly, these preclinical findings have demonstrated merit in clinical studies. The abscopal effect has been recognized in combination with CTLA-4 blockade in melanoma [41] and NSCLC [42]. A recent retrospective study of melanoma patients also identified that RT + ipilimumab resulted in almost a doubling of OS and abscopal events were present in about 20% of patients [43]. The results of these clinical findings are encouraging and improved outcomes are likely as a more thorough understanding of the relationship between RT and immunotherapy evolves.

The organ(s) at risk in the treatment region must also be taken into consideration when combining RT with immunotherapy. In the setting of consolidative thoracic radiation therapy for SCLC, the most critical structure is the normal surrounding lung. This is important as both RT and immunotherapy separately have been shown to cause pneumonitis. Preclinical data of partial volume lung RT in rats revealed cytokine and immune cell responses were initiated at 1 hr following treatment and cyclic patterns of these responses were sustained up to sixteen weeks [44]. How these inflammatory responses induced by RT in the lung influence toxicity with immunotherapy are not known, but clinical data suggests that RT combined with immunotherapy may not lower the tolerance of the lung too drastically.

A retrospective study evaluating 16 patients with NSCLC who were prospectively enrolled in a phase 2 trial with phased ipilimumab and chemotherapy identified that adjuvant RT did not lead to any grade  $\geq 3$  toxicity [45]. Additionally, NSCLC patients that received RT followed by nivolumab [46] or a single patient in a case report who received concurrent RT and ipilimumab [42] did not have increased lung toxicity. Finally, a recent retrospective report of melanoma patients also indicated that patients that received RT before, during or after ipilimumab had no increased toxicity in the lung [43]. Combining RT, which can instigate a robust immune response, with checkpoint inhibition may provide synergism in immune-mediated destruction of SCLC tumors. By treating intrathoracic disease with consolidative RT after standard of care chemotherapy, the targeted tumor burden will be low and this may be the optimal time to amplify synergism between RT and immunotherapy.

### **1.1.7 Rationale to Support Nivolumab Monotherapy “Flat” Dose of 480 mg Every 4 Weeks**

Nivolumab monotherapy has been extensively studied in NSCLC patient populations and in other solid tumor indications with body weight-normalized dosing (mg/kg). Nivolumab pharmacokinetics (PK) and exposures of participants in these studies have been characterized by population pharmacokinetic (PPK) analysis of data collected in these studies, together with PK data from several phase I, II, and III clinical studies of nivolumab monotherapy in solid tumors. Nivolumab PK was determined to be linear, with dose proportional exposures over a dose range of 0.1 to 10 mg/kg. Nivolumab clearance and volume of distribution were found to increase with increasing body weight, but the increase was less than proportional, indicating that a mg/kg dose represents an over-adjustment for the effect of body weight on nivolumab PK. Conversely, given the relationship between nivolumab PK and body weight, a flat dose is expected to lead to lower exposures in heavier patients, relative to the exposures in lighter patients. It should be noted that a dose of 480 mg nivolumab across typical body weights leads to peak nivolumab concentrations that are less than 10mg/kg which has been previously shown to be safe and well tolerated across multiple clinical studies. Based on clinical modeling and simulation approaches using population PK (PPK) and exposure analyses of data from studies in multiple tumor types, a dose of 480mg delivered every 4 weeks is expected to be similarly efficacious compared to previously utilized dose strategies including 3mg/kg delivered every 2 weeks or 240mg flat dose delivered every 2 weeks.

Nivolumab monotherapy has been extensively studied in multiple tumor types with body weight normalized dosing (mg/kg). Nivolumab PK was determined to be linear, with dose proportional exposures over a dose range of 0.1 to 10 mg/kg. Nivolumab clearance and volume of distribution was found to increase with increasing body weight, but the increase was less than proportional indicating that a mg/kg dose represents an over-adjustment for the effect of body weight on nivolumab PK. Flat dosing is expected to reduce prescription dosing errors, shorten pharmacy preparation time, and improve ease of administration. Extending the dosing interval to 4 weeks provides numerous benefits to patients including increased flexibility between clinical visits,

as compared to a 2 week dosing schedule. A flat dose of 480 mg every 4 weeks was selected based on equivalence to the approved 3 mg/kg every 2 weeks at the median body weight of ~ 80 kg in nivolumab-treated subjects. A PPK model predicted overall nivolumab average exposures across subjects with a wide range of body weight from 480 mg Q4W to be similar to that from 3 mg/kg Q2W. Although the flat dose is expected to lead to higher exposure in lighter patients relative to the exposure in heavier patients given the relationship between nivolumab PK and body weight, the predicted median and 95th percentile of exposures are maintained below those in 10 mg/kg every 2 weeks, which was established as a safe and well-tolerated dose across multiple tumor types. There was no clinically meaningful relationship between nivolumab exposure or body weight and frequency or severity of adverse events. Therefore, a flat dose of 480 mg every 4 weeks is expected to be safe and tolerable in patients. In terms of efficacy, 480 mg every 4 weeks is expected to result in similar efficacy given a flat exposure-response relationship and same dose intensity. Overall, the benefit-risk profile of nivolumab 480 mg Q4W is expected to be similar to the approved regimen 3 mg/kg Q2W, and it is recommended for further investigation in this study. Additionally, this simplified dose strategy will limit the number of visits and overall treatment administration inconvenience.

Taken together, the PK, safety, and efficacy data indicate that the safety and efficacy profile of 480 mg nivolumab every 4 weeks will be similar to that of 3 mg/kg nivolumab every 2 weeks. Based on these clinical results, a flat dose of 480 mg every 4 weeks will be utilized for the maintenance dosing following completion of nivolumab/ipilimumab combination.

### **1.1.8 Rationale for Permitting Continued Treatment in Select Cases of Progressive Disease**

Accumulating clinical evidence indicates some patients treated with immune system stimulating agents may develop progression of disease (by conventional response criteria) before demonstrating clinical objective responses and/or stable disease. This phenomenon was observed in a phase I study of nivolumab [47] and also in combination with ipilimumab [48]. Two hypotheses have been put forth to explain this phenomenon. First, enhanced inflammation within tumors could lead to an increase in tumor size, which would appear as enlarged index lesions and as newly visible small non-index lesions. Over time, both the malignant and inflammatory portions of the mass may then decrease leading to overt signs of clinical improvement. Alternatively, in some individuals, the kinetics of tumor growth may initially outpace anti-tumor immune activity.

With sufficient time, the anti-tumor activity will dominate and become clinically apparent. Therefore participants will be allowed to continue study therapy after initial investigator-assessed Response Evaluation Criteria in Solid Tumors (RECIST 1.1)-defined progression if they are assessed to be deriving clinical benefit and tolerating study drug. Such participants must discontinue study therapy upon evidence of further progression.

## **1.2 Background**

### **1.2.1 Nivolumab Mechanisms of Action**

Nivolumab is a fully humanized, IgG4 (kappa) isotype monoclonal antibody (mAb) that binds PD-1 on activated immune cells and disrupts engagement of the receptor with its ligands PD-L1 (B7-H1/CD274) and PD-L2 (B7-DC/CD273), thereby abrogating inhibitory signals and augmenting the host antitumor response. PD-

1, (CD279), a 55-kDa type I transmembrane protein, is a member of the CD28 family of T-cell co-stimulatory receptors that also includes CD28, CTLA 4, ICOS, and BTLA. PD-1 contains an intracellular membrane proximal immunoreceptor tyrosine inhibitory motif (ITIM) and a membrane distal immunoreceptor tyrosine-based switch motif (ITSM). Two ligands specific for PD-1 have been identified: PD-L1 (B7-H1/CD274) and PD-L2 (B7-DC/CD273). PD-L1 and PD-L2 have been shown to down-regulate T cell activation on binding to PD-1 in both murine and human systems. PD-1 delivers a negative signal by the recruitment of SHP-2 to the phosphorylated tyrosine residue in the ITSM in its cytoplasmic region. PD-1 is primarily expressed on activated T cells, B cells, and myeloid cells. Further evidence for a negative regulatory role of PD-1 comes from studies of PD-1-deficient mice. PD-1-deficient mice develop various autoimmune phenotypes, including dilated cardiomyopathy, a lupus-like syndrome with arthritis and nephritis, and accelerated diabetes mellitus. The emergence of these autoimmune phenotypes is dependent on the genetic background of the mouse strain, and many of these phenotypes emerge at different times and show variable penetrance. In addition to the phenotypes of null mutations, PD-1 inhibition by antibody-mediated blockade in several murine models has been found to play a role in the development of autoimmune diseases such as encephalomyelitis, graft-versus-host disease, and type I diabetes. Taken together, these results suggest that PD-1 blockade has the potential to activate anti-self T-cell responses, but these responses are variable and dependent on various host genetic factors. Thus, PD-1 deficiency or inhibition is not accompanied by a universal loss of tolerance to self-antigens.

Preclinical animal models of tumors have shown that blockade by PD-1 by mAbs can enhance the anti-tumor immune response and result in tumor rejection. Antitumor activity by PD-1 blockade functions in PD-L1-positive tumors as well as in tumors that are negative for the expression of PD-L1. This suggests that host mechanisms (i.e., expression of PD-L1 in antigen-presenting cells) limit the antitumor response. Consequently, both PD-L1 positive and negative tumors may be targeted using this approach. In humans, constitutive PD-L1 expression is normally limited to macrophage-lineage cells, although expression of PD-L1 can be induced on other hematologic cells as well, including activated T cells. However, aberrant expression of PD-L1 by tumor cells has been reported in a number of human malignancies. PD-L1 expressed by tumor cells has been shown to enhance apoptosis of activated tumor-specific T cells *in vitro*. Moreover, the expression of PD-L1 may protect the tumor cells from the induction of apoptosis by effector T cells. Additional details are available in the Nivolumab Investigator Brochure.

## **1.2.2 Ipilimumab Mechanisms of Action**

Ipilimumab is a fully humanized, IgG1 (kappa) isotype mAb that binds to the CTLA-4 antigen expressed on a subset of T cells from human and nonhuman primates. CTLA-4 is a negative regulator of T-cell activity. Ipilimumab binds to CTLA-4 and blocks the interaction of CTLA-4 with its ligands, CD80/CD86. Blockade of CTLA-4 has been shown to augment T-cell activation and proliferation, including the activation and proliferation of TILs. Inhibition of CTLA-4 signaling can also reduce Treg cell function, which may contribute to a general increase in T-cell responsiveness, including the anti-tumor response.

## **1.2.3 Product Development Background**

Nivolumab is in clinical development for the treatment of patients with NSCLC, RCC, glioblastoma, and other cancer types. Recently, nivolumab was approved by the FDA for the treatment of patients with advanced

NSCLC and melanoma. Nivolumab is also approved for the treatment of advanced melanoma in Europe, Japan, and other countries.

In the phase I/II trial (CA209-032), in participants with heavily pretreated SCLC, nivolumab monotherapy showed an ORR of 10%, whereas the combination of nivolumab-1 and ipilimumab-3 demonstrated an ORR of 30% [23]. Study CA209-451 is the second phase III study in the clinical development program for nivolumab in SCLC and will evaluate the efficacy and safety of nivolumab monotherapy and nivolumab and ipilimumab combination therapy, as maintenance treatment following first line platinum-based chemotherapy in patients with ED-SCLC.

## **1.3 Research Hypothesis**

For patients with ED-SCLC and at least stable disease after 4 to 6 cycles of platinum-based chemotherapy, we hypothesize that ipilimumab and nivolumab with thoracic radiation therapy (30 Gy in 10 fractions) will improve 6-month PFS by at least 20% compared with a 6-month historical PFS rate of 24% among patients treated in a similar fashion without combined checkpoint blockade [5].

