#### **4.2.1 Study Phases**

The study is divided into the following phases: Screening, Treatment, and Follow-up.

The study calendar is outlined in Appendix 1.

**1. Screening:** Screening begins after the participant signs the informed consent form (ICF) and is enrolled on the study through the Moffitt Clinical Research Network (MCRN) at Moffitt Cancer Center.

- Whenever possible, tumor tissue (archival or recent tumor biopsy 10 slides or tissue block) should be submitted to the central lab for correlative studies. Participants must consent to allow the acquisition of tumor tissue by study personnel for performance of the correlative studies.
- Baseline assessments must be performed within the timeframes described in Table 7.1-1.
- For patients with known brain metastases at presentation, brain radiotherapy (whole brain radiation therapy (WBRT) or stereotactic radiation) may be offered, per local standard of care. Patients with asymptomatic brain metastases at initial diagnosis may be treated with chemotherapy alone at the discretion of the patient's treating physician. A 4 week disease stable interval as confirmed by MRI or CT brain w/ contrast (Table 7.4-2) is required after treatment of brain metastases before initiation of thoracic radiation therapy.
- Prophylactic Cranial Irradiation (PCI) is not allowed.
- Treatment initiation must be  $> 3$  weeks but  $\leq 8$  weeks from the last dose of chemotherapy for all participants.
- The screening phase either ends with confirmation of full eligibility and initiation of study treatment or with the confirmation that the participant is a screen failure.
- This study permits the re-enrollment of a participant that has discontinued the study as a pretreatment failure before enrollment. If re-enrolled, the participant must be reconsented. A new participant identification number will be assigned at the time of re-enrollment.

**2. Treatment:** The treatment phase begins with a study initiation call to the MCRN. Treatment is to begin within 3 business days of study initiation.

Study therapy is administered as described in Tables 5.2-1 and 6.5-1 until disease progression, discontinuation due to toxicity, withdrawal of consent, the study ends, or other criteria for discontinuation are met, as described in Section 4.6 and Section 6.5.3.4. Patients may be treated beyond initial progression as specified in Section 6.5.5.

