## 2. Target Population

- a) Patients with SCLC documented by histology or cytology from brushing, washing, or needle aspiration of a defined lesion, but not from sputum cytology alone;
- b) Participants must have presented at initial diagnosis with extensive-stage disease (defined as Stage IV (T any, N any, M1a/b) per NCCN Guidelines Version 1.2015, AJCC Cancer Staging Manual, 7th Edition, 2010);
- c) Eastern Cooperative Oncology Group (ECOG) Performance Status (PS) 0 or 1 (see <http://ecog-acrin.org/resources/ecog-performance-status> for details)
- d) Participants must have received 4-6 cycles of platinum-based first-line chemotherapy and must have an ongoing response of complete response (CR), partial response (PR), or stable disease (SD) after completion of chemotherapy. Acceptable combinations, as recommended per NCCN guidelines, include cisplatin or carboplatin combined with either etoposide or irinotecan;
  - i) As an exception to the above criterion, participants receiving only 3 cycles of chemotherapy due to toxicity are eligible, if they have an ongoing PR or CR after the 3rd cycle
  - ii) Participants who have received > 6 cycles of platinum-based first-line chemotherapy are not eligible
- e) Participants must initiate study treatment with thoracic radiation therapy  $\leq$  8 weeks (56 days) from the last dose of platinum-based first line chemotherapy;
  - i) Thoracic radiation therapy must not be administered < 3 weeks (21 days) from the last dose of platinum-based first line chemotherapy
  - ii) Ipilimumab/nivolumab study therapy must not be administered < 13 days and not more than 21 days from the last dose of thoracic radiotherapy
- f) Whenever possible, a formalin-fixed, paraffin-embedded (FFPE) tumor tissue block or 10 unstained slides of tumor sample (archival or recent) for biomarker evaluation should be made available and submitted to the central lab for correlative studies;
- g) Patient re-enrollment: This study permits the re-enrollment of a participant who has discontinued the study due to pre-treatment failure (ie, participant has not been treated). If re-enrolled, the participant must be re-consented.

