## 9.2 Phase I/II Sample Size Determination

We propose a single arm, non-randomized phase I/II study, with the goal to evaluate efficacy compared to historical controls. Slotman et al. [5] reported a 6-month progression-free survival (PFS) of 24% with platinum-based chemotherapy and thoracic radiation therapy. We would propose to pursue a phase III randomized controlled study if there is a 20% improvement in 6-month PFS with the addition of combined immune checkpoint blockade as part of the proposed clinical study. Therefore, this regimen would be considered not worthwhile to pursue if the true 6-month PFS is 24% or less and worth pursuing if the true 6-month PFS is 44% or greater. The trial will use a Simon's 2-stage design[49] with 1-sided 0.05 level type I error and 90% power. The total target sample size is 52 patients. During the 1st stage, 18 patients will be accrued. If 4 or fewer patients have not progressed at 6 months, the study will be closed for futility. However, if at least 5 patients have not progressed at 6 months, then the study will continue to accrue an additional 34 patients. Once the total number of patients has accrued (n=52), then the null hypothesis will be rejected if at least 18 patients have not progressed at 6 months. In order to accommodate censoring, we may increase the total sample size by up to 10% (n=57).

- The final PFS analysis is targeted to occur 6 months after the last participant is enrolled
- The final OS analysis is targeted to occur 1 year after the last participant is enrolled.

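### The 24% benchmark comes from patients who had responded to chemotherapy and all received PCI, so a test against it does not isolate the effect of adding checkpoint blockade

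*Combined protocol and SAP*

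**What the plan says.** Section 1.3 sets the hypothesis against a "6-month historical PFS rate of 24% among patients treated in a similar fashion without combined checkpoint blockade". The Introduction likewise calls the historical cohort similar. Section 9.2 takes the 24% from the phase III thoracic radiotherapy trial. The regimen is "not worthwhile to pursue if the true 6-month PFS is 24% or less" and "worth pursuing if the true 6-month PFS is 44% or greater", tested by a Simon two-stage design with "1-sided 0.05 level type I error and 90% power". Section 9.2 describes the 20-point difference as a gain from adding combined checkpoint blockade and makes it the trigger for a randomised phase III trial.

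Section 1.1.4 describes the source of the 24%. In that trial, "participants who had any response to systemic 4-6 cycles of EP chemotherapy were enrolled", and "All patients also received prophylactic cranial irradiation as part of the study protocol".

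For the present trial, section 4.2.1 states that "Prophylactic Cranial Irradiation (PCI) is not allowed", and section 1.1.5 gives the clinical reasons. Under section 4.4.1 (Target Population), participants "must have an ongoing response of complete response (CR), partial response (PR), or stable disease (SD") after chemotherapy. Section 4.2 also names stable disease as qualifying.

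Section 9.5.2 plans overall Kaplan-Meier estimates only. No section adjusts the 24% for these differences, gives a range for it, or limits the attribution.

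**The concern.** A single-arm test can credit a gain to the added drugs only if the benchmark is the rate this population would have had without them. By the protocol's own account, the benchmark cohort differs in one treatment (PCI) and in one entry criterion (response to chemotherapy). Either could move 6-month PFS independently of nivolumab and ipilimumab. PFS in section 9.4.1 counts first progression with no exception for the brain, so a difference in PCI bears directly on the primary endpoint.

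At stake is how the result is read. A pass or a fail against 24% could partly reflect PCI omission or case mix, yet sections 1.3 and 9.2 would have it read as the contribution of checkpoint blockade and use it to decide on phase III.

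**Working it through.** **Cohorts side by side**

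| Feature | Source of the 24% (section 1.1.4) | This trial |
|---|---|---|
| PCI | All patients | Barred (1.1.5, 4.2.1) |
| Status after chemotherapy | Any response | CR, PR or SD (4.2, 4.4.1) |
| Thoracic RT | 30 Gy in 10 fractions | 30 Gy in 10 fractions (4.2, 5.1) |

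The thoracic radiotherapy matches; the first two rows do not.

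**Inputs (section 9.2).** Null 0.24 and alternative 0.44. Stage 1 has 18 patients and continues if at least 5 are progression-free at 6 months. The total is 52 (34 more), and the null is rejected if at least 18 are progression-free. Sections 4.2 and 9.2.1 give a total of 50; that is a separate inconsistency, and the 52-patient rule is used here.

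**Formula.** For a true 6-month rate p,

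P(reject) = sum over x = 5 to 18 of P[Bin(18, p) = x] × P[Bin(34, p) ≥ 18 − x].

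**Reproducing the plan's figures.**
- p = 0.24: probability of early stopping 0.559, P(reject) = 0.0494, within the nominal 0.05.
- p = 0.44: probability of early stopping 0.049, P(reject) = 0.9035, matching 90% power.

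The design is therefore correct for the hypothesis that it states.

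**If the rate without checkpoint blockade here is not 24%.** The documents give no alternative rate, so those below are assumptions. The rule is unchanged.

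| Assumed rate without the drugs | P(positive trial), no drug effect | Rate after a true +20 points | P(positive trial) at that rate |
|---|---|---|---|
| 18% | 0.0028 | 38% | 0.6937 |
| 20% | 0.0087 | 40% | 0.7822 |
| 22% | 0.0224 | 42% | 0.8520 |
| 24% | 0.0494 | 44% | 0.9035 |
| 26% | 0.0951 | 46% | 0.9393 |
| 28% | 0.1628 | 48% | 0.9630 |
| 30% | 0.2524 | 50% | 0.9779 |

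The chance of a positive trial with no drug effect passes 0.05 at a rate of 24.03% and reaches 0.10 at 26.2%. The rule has almost no slack above 24%.

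**The case against.** The strongest defence is that section 9.2 defines its error rates for a fixed pair of rates, for which they are correct, and that section 2.1.2 states the phase II objective as estimating 6-month PFS, not isolating a drug effect. Non-comparability is an inherent limit of single-arm phase II trials, and a randomised phase III would settle attribution. All of this stands, and it is why the primary rule should not change. It does not cover the statement in 1.3 that the cohorts were similarly treated, or the wording in 9.2 that credits the gain to the added drugs.

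Four stronger readings are tempting but not supported:

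- *The trial is mis-sized or its error rates are wrong.* They reproduce. The 78% figure is power at a true rate of 40%; section 9.2 promises 90% only at 44% or above.
- *Scheduled brain MRI is a further difference from the source trial.* Brain surveillance is a feature of this trial (Weeks 10 and 23 fall within 6 months in Table 7.4-2), but no section says whether the source trial imaged the brain. The criticism of missing brain imaging in section 1.1.5 concerns a different trial, of PCI.
- *The bias runs in a known direction.* Omitting PCI and admitting stable disease would plausibly lower the rate without the drugs, while brain imaging at entry could raise it by excluding occult disease. The documents do not settle the net effect.
- *Not counting brain progression found only on scheduled MRI would restore comparability.* It would remove events from this trial alone and could only raise the estimate. It would also need later extracranial scans, which sections 4.2.1 and 7.4 do not schedule after progression in patients who stop treatment.

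**Conclusion.** The point holds as a limit on interpretation. The differences in PCI and response status are documented by the protocol itself, so the claim of similar treatment and the attribution of a 20-point gain to checkpoint blockade are unsupported as written. The type I error of 0.049 and power of 90% belong to the test of 24% against 44%; they are not established for the effect of the added drugs.

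For scale, a shift of four points in the rate without the drugs moves the chance of a positive trial with no drug effect from 4.9% to 0.9% (at 20%) or 16% (at 28%). Power for a 20-point gain moves from 90% to 78% or 96%. These rates are illustrative and are not derived from PCI or stable disease. The conclusion also relies on section 1.1.4's description of the source trial.

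**What to change.** Keep the primary decision rule.

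1. In sections 1.3 and 9.2, replace the claim of similar treatment with the two stated differences: PCI given to all source patients but barred here, and stable disease admitted here. Add that rejecting the null is evidence against a fixed 24% benchmark, not a measure of the effect of checkpoint blockade.
2. In section 9.5.2, pre-specify a supportive Kaplan-Meier estimate of 6-month PFS with 95% CI for participants entering with CR or PR, and show those entering with SD separately.
3. Extend the exploratory endpoint in section 9.4.3, which already covers progression in the thorax, brain and other sites, to tabulate first progression by 6 months as brain-only or extracranial.

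The cost is a few lines of text and some extra tables. Response status is needed for eligibility, and site of progression is already an exploratory endpoint. The CR/PR subset will be smaller and less precise, so it should stay supportive. No analysis here can undo the PCI difference, which remains a stated limitation.
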